7.1.7 Injection and scanning

The volume of contrast agent, the volume of saline follow-up injection and the dose, the number and frequency of injector usage, the sequence type (standard vs modified, coded specific sequence type), the reason for modified sequence will be analysed for all patients (FIP), by site (CSP), by country (CSP), by specialty (SPP), by GBCA (GBCAP), by scanner type (FIP), by scanner field strength (FIP) and by scan modality (MRA/MRI).

The sequence type will additionally be analysed by injection protocol for all patients (FIP), by site (CSP), by weight (FIP) and by country (CSP).

The mean volume of contrast agent and the volume of saline follow-up injection will be shown in a bar chart for type of sequence.

The dose in mmol/kg will be calculated according to

$$\text{Dose} = \text{injected volume} * \text{GBCA concentration} / \text{weight}$$

Where GBCA concentration = 1 mmol/mL for Gadovist and
 0.5 mmol/mL for all other GBCA

Dose will also be analysed for the following categorisation:

≤0.1, > 0.1 to 0.2, > 0.2 to 0.3 and >0.3 mmol/kg

for all patients (FIP), by GBCA (GBCAP), by age groups (FIP), by GFR rate (GFRP), and by indication (see 3.2.1.5).

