3.2.1.5 MR Examination

- Organ/system under examination (brain/meninges/spinal cord, head and neck, breast, bronchial tissue/lungs, cardiovascular, renal, hepatobiliary, pancreas, gastrointestinal tract, urinary tract incl. bladder, genital tract incl. gonads, endocrine glands, musculoskeletal system incl. bones/joints/muscles, lymphoid tissue incl. blood disorders, whole body, other)
- Indication (CNS indication [brain/meninges/spinal cord], organ/whole body [all other organs (if not MRA like a cardiovascular MRA)], angiography [any MRA])
- MRI details (if applicable)
 - Brand of contrast agent
 - Volume of contrast agent (ml)
 - Injector use (yes/no)
 - Volume of saline follow-up injection (none or in mL)
 - Scanner make (GE, Siemens, Philips, other)
 - Field strength (1.5T, 3T, >3T)
 - Scanner model
 - Scan modality (dynamic, delayed, both dynamic and delayed)

- Type of sequence/protocol (standard, modified)
 - If modified, reason for modifying the sequence (improvement of image quality, removal of artifacts preventing a diagnostic image, patient related reason, other)
- MRA details (if applicable)
 - Brand of contrast agent
 - Volume of contrast agent (ml)
 - Injector use (yes/no)
 - Volume of saline follow-up injection (none or in mL)
 - Scanner make (GE, Siemens, Philips, other)
 - Field strength (1.5T, 3T, >3T)
 - Scanner model
 - Scan modality (dynamic, delayed, both dynamic and delayed)
 - Type of sequence/protocol (standard, modified)
 - If modified, reason for modifying the sequence (improvement of image quality, removal of artifacts preventing a diagnostic image, patient related reason, other)
- MRA or MRI part of a broader pathway to clarify the illness under investigation (yes, no)
- Any other image scan before the MR scan in relation to the illness under investigation (none, CT, ultrasound, CE-MR, liver-specific MR, non-CE-MR, SPECT, PET, X-ray (excluding CT), other)

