3.2.2 Investigator data

- Date of first patient
- Date of last patient
- Total number of patients visited by this investigator during the study period
- Number of procedures performed by the investigator (liver-specific MR, Non-CE MR, CE-MRI, CE-MRA, CT, ultrasound, PET-PET/CT-PET/MR, SPECT, X-ray, other)

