6 ANALYSIS SETS

The allocation of subjects to analysis sets will be determined by the sponsor and the CRO on a per-subject basis immediately before data base lock.

Full eligible population (FEP)

The FEP population consists of all screened subjects, both successful and failed screens.

Full included population (FIP)

The FIP population consists of all successful screens.

Safety population (SAF)

The SAF population consists of all patients with a documented MRI/MRA procedure.

Population by country/site (CSP)

The CSP population consists of all successful screens in with known country/site.

Population by GBCA type (GBCAP)

The GBCA population consists of all subjects with known GBCA brand type.

Population by speciality (SPP)

The SPP population consists of all subjects examined for an ailment with known speciality.

Population by GFR rate (GFRP)

The GFR population consists of all subjects with known range of GFR rate.

Population by History of allergy (HISALP)

The history of allergy population consists of all subjects with known history of allergy status.

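### The dose derivation gives every agent except Gadovist a default concentration of 0.5 mmol/mL, which misstates mmol/kg for any recorded brand with a different concentration

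*SAP*

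**What the plan says.** Section 7.1.7 of the SAP introduces the derivation with "The dose in mmol/kg will be calculated according to" and then gives dose as injected volume times concentration divided by weight. Two constants complete it: "Where GBCA concentration = 1 mmol/mL for Gadovist and" "0.5 mmol/mL for all other GBCA". There is no table of brands, no further exception, and no rule for a brand that is unknown or unexpected.

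The inputs are in section 3.2.1: weight in kg, and for each MRI or MRA the items "Brand of contrast agent" and volume in mL. Concentration is not among the listed variables. The analysis set for by-brand results excludes no agent: "The GBCA population consists of all subjects with known GBCA brand type".

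The derived dose is summarised under Injection and scanning (Tables 7.1 to 7.8). It is also grouped as "≤0.1, > 0.1 to 0.2, > 0.2 to 0.3 and >0.3 mmol/kg" overall and by GBCA, indication, age group and GFR rate (Tables 7.16 to 7.20).

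**The concern.** A default constant is safe only if it is known to be right for everything it covers. Here its coverage is not bounded. Section 1.1 asks at what dosages radiologists use the agents on their own market, and section 3.1 plans up to 5400 patients from 7 countries and 14 sites. The SAP itself accepts that concentration varies by brand, since it makes an exception for one. Without a recorded concentration, a wrong constant cannot be detected from the variables the SAP lists.

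Dosage is the opening question of the rationale, and pattern of use is the primary objective. An error in the constant would not behave like noise. It would multiply every dose of one brand by the same factor and so look like a difference in practice between brands. Section 7 plans exploratory ANOVA and chi-square tests for stratified comparisons, including by GBCA, and section 5.8 calls p < 0.05 significant. A coding artefact could therefore be reported as a significant brand difference.

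**Working it through.** **Inputs from the SAP.** Dose = V × C / W, with V in mL, C in mmol/mL and W in kg (section 7.1.7). C = 1 for Gadovist and 0.5 for all others. The category cut points are 0.1, 0.2 and 0.3 mmol/kg.

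**Inputs assumed.** The SAP states no other concentration, so c = 0.25, 0.5, 0.75 and 1.0 mmol/mL are used as an illustrative range for an agent not named Gadovist. The 70 kg weight and the volumes below are also illustrative.

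**Check of the rule as written.** The SAP gives no worked dose to reproduce. The units are sound: mL × mmol/mL / kg = mmol/kg. At 70 kg, 14 mL at 0.5 gives 14 × 0.5 / 70 = 0.100, and 7 mL at 1.0 gives 7 × 1.0 / 70 = 0.100. The rule is correct for agents that have the coded concentrations.

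**Error when the true concentration is c.** Reported / true = (V × 0.5 / W) / (V × c / W) = 0.5 / c. Volume and weight cancel, so the factor is the same for every patient given that brand.

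| Assumed c (mmol/mL) | 0.5 / c | Error |
|---|---|---|
| 0.25 | 2.00 | +100% |
| 0.5 | 1.00 | none |
| 0.75 | 0.67 | −33% |
| 1.0 (brand other than Gadovist) | 0.50 | −50% |

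**Effect on the dose categories.**

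| Assumed c | True dose (mmol/kg) | Reported dose | Category change |
|---|---|---|---|
| 0.25 | 0.025 | 0.050 | none, stays ≤0.1 |
| 0.25 | 0.05 | 0.10 | none, stays ≤0.1 |
| 0.25 | 0.10 | 0.20 | ≤0.1 to >0.1–0.2 |
| 0.25 | 0.20 | 0.40 | >0.1–0.2 to >0.3 |
| 0.75 | 0.15 | 0.10 | >0.1–0.2 to ≤0.1 |
| 1.0 | 0.20 | 0.10 | >0.1–0.2 to ≤0.1 |

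The mean dose for the brand is wrong by the full factor in every case except c = 0.5. The categories change only when the factor carries a dose across a cut point.

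**Unknown brand.** Dose is analysed for all FIP patients, whereas GBCAP needs a known brand, so unknown brands are foreseen. A program coded as Gadovist, otherwise 0.5, would give them 0.5. If the agent was in fact Gadovist, 7 mL in 70 kg would be reported as 7 × 0.5 / 70 = 0.050 instead of 0.100. Section 5.5, under which missing values are not replaced, argues against that coding, but section 7.1.7 does not rule it out.

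**The case against.** The strongest reply is that the SAP does not show any error occurring. It names no agent with a third concentration, and if all brands other than Gadovist are 0.5 mmol/mL the default does no harm. That stands, and it makes the point conditional.

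Some stronger readings are tempting, but the document does not support them:

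- **Liver-specific agents.** A reader might infer from "Number of procedures performed by the investigator (liver-specific MR, Non-CE MR, CE-MRI, CE-MRA" that such agents are in the brand data. In sections 3.2.2 and 3.2.3 this item is only a workload count, listed apart from CE-MRI and CE-MRA. In section 3.2.1.5 it is a type of prior scan. Hepatobiliary as an organ option identifies no agent.
- **Free-text brand.** The SAP gives no field format, and the case report form may hold a pick-list. All that can be said is that the SAP lists no permitted brands.
- **False organ differences.** Table 7.18 is by indication, in three groups (CNS, organ/whole body, angiography), and not by organ.
- **Missing session total.** Brand and volume are listed separately for MRI and MRA, and one might infer that combined doses are lost. Dose is already shown by scan modality, and nothing shows that patients receive two injections. This is a separate clarification.

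It is also fair to say that the study is descriptive, that volume in mL is reported by GBCA and does not depend on the constant, and that a wrong factor could be corrected in programming. These limit the damage but are no reason to leave an unverified default in the derivation.

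**Conclusion.** The point holds in conditional form. The SAP fixes one concentration for an unbounded set of agents and provides no check on it. Any recorded brand with c other than 0.5 mmol/mL would have all its doses misreported by 0.5/c, between half and twice the true value over the assumed range of 0.25 to 1.0 mmol/mL. Tables 7.5 and 7.17 would show this most directly, as a spurious brand difference. Whether any result changes depends on the brands in the database, which the SAP does not list; if all others are 0.5 mmol/mL, nothing changes. Because the harm is possible but not shown, this is a should-fix and not a must-fix. It concerns only how the administered dose is derived, not which dose is right.

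**What to change.** Before database lock, list the brands in the database and replace the catch-all in section 7.1.7 with a look-up table giving the labelled concentration of each. For any brand that is unknown or not in the table, set dose to missing and raise a query; do not default to 0.5.

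The cost is a short table in the SAP, one format in the program and possibly a few missing doses. No new data collection is needed. If the table confirms 0.5 mmol/mL for every brand other than Gadovist, the results for patients with a known brand stay as they are and the derivation is documented.

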1 INTRODUCTION

1.1 Rationale for study

It is currently unknown and of high scientific interest with which dosages the radiologists use the gadolinium-containing contrast media currently available in their market. Such information, which is very important for the referring physicians, can only be obtained by up-to-date observation and documentation in the daily routine.

It is also currently unknown and of further interest for the assessment of the applications, which criteria referrers consider for the administration of gadolinium-containing contrast agents after the publication of the EMA/457616/2017 requirements. In particular, it is unknown whether the presence of pre-existing renal insufficiency is taken into consideration, how often MR contrast agents are used in the same patient and whether this is dependent on indication and/or comorbidities. For example, this question is relevant to patients evaluated for multiple sclerosis and cancers, where it is unknown if notwithstanding the known brain retention of gadolinium, repeated contrast enhanced MR scans are considered necessary. Also, it is unknown if dose reductions, perhaps dependent on scanner magnetic field strength, are applied.

The study plan/protocol and the resulting documentation sheet of the requested study accurately collects data useful to clarify these points and will therefore provide more accurate insight into the potentially adapted clinical procedure.

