7 STATISTICAL METHODS

All continuous variables will be summarized using the following descriptive statistics: n (non-missing sample size), mean, standard deviation, median, minimum and maximum. The frequency and percentages (based on the non-missing sample size) will be reported for categorical measures. Data that will be listed will be sorted by country, site and subject.

For the comparison of endpoints in stratified analyses (e.g. by country, by GBCA etc.) explorative statistical tests will be applied (ANOVA for continuous endpoints, Chi-Square tests for categorical endpoints) if feasible.

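### The dose categories in SAP 7.1.7 do not resolve doses at or below 0.1 mmol/kg, and by GFR, age group and indication only these categories are planned

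*SAP*

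**What the plan says.** SAP 1.1 gives the dosages in use as a main reason for the study. On reductions it says: "Also, it is unknown if dose reductions, perhaps dependent on scanner magnetic field strength, are applied". The same section asks whether pre-existing renal insufficiency is taken into account.

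SAP 7.1.7 plans two analyses of dose.

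- **Uncategorised dose.** "The volume of contrast agent, the volume of saline follow-up injection and the dose" are analysed overall, by site, country, specialty and GBCA, and "by scanner type (FIP), by scanner field strength (FIP) and by scan modality (MRA/MRI"). Under SAP 7, continuous variables are summarised by "n (non-missing sample size), mean, standard deviation, median, minimum and maximum".
- **Categorised dose.** "Dose will also be analysed for the following categorisation": "≤0.1, > 0.1 to 0.2, > 0.2 to 0.3 and >0.3 mmol/kg". The strata are "for all patients (FIP), by GBCA (GBCAP), by age groups (FIP), by GFR rate (GFRP), and by indication". Field strength is not among them.

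Dose is derived as injected volume times concentration divided by weight. Concentration is 1 mmol/mL for Gadovist and 0.5 mmol/mL for every other agent.

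**The concern.** All three cut-points separate doses from 0.1 upwards, and none separates doses below 0.1. A reduction that starts at or below 0.1 therefore leaves the patient in the same cell. The gap is widest for GFR, age group and indication, where 7.1.7 plans nothing but the categories. GFR is the stratum that bears on the renal question in 1.1, so Table 7.20 could look the same whether or not doses below 0.1 were reduced in patients with impaired renal function.

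The boundary is a second problem. Dose is a ratio of a recorded volume to a recorded weight, and the cut lies exactly on 0.1. Patients intended to receive the same dose per kg can land in different bins because of rounding. SAP 7 applies exploratory chi-square tests to categorical endpoints across strata, so a difference in rounding between agents of different concentration could read as a difference in dosing.

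**Working it through.** The SAP gives no figure of its own to reproduce here. The inputs from 7.1.7 are the cut-points (0.1, 0.2, 0.3 mmol/kg), the dose formula and the two concentrations. An intended dose of 0.1, the weights and the rounding steps are assumptions made for illustration.

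**1. What the lowest bin hides.** Doses of 0.025, 0.05, 0.075, 0.09 and 0.1 all fall in ≤0.1. Take a stratum dosed at exactly 0.1 and let a share *s* receive 0.05. The mean is 0.1(1 − *s*) + 0.05*s*.

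| Share at 0.05 | Percentage in ≤0.1 | Mean dose | Minimum |
|---|---|---|---|
| 0% | 100% | 0.100 | 0.10 |
| 10% | 100% | 0.095 | 0.05 |
| 30% | 100% | 0.085 | 0.05 |
| 50% | 100% | 0.075 | 0.05 |

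The categories do not move, while the mean and minimum do.

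**2. What the continuous summary leaves open.** A mean of 0.095 arises from 10% at 0.05 (0.9 × 0.1 + 0.1 × 0.05) and equally from 20% at 0.075 (0.8 × 0.1 + 0.2 × 0.075). The median is 0.1 in both. The SD and minimum differ in so clean an example, but neither states what proportion had a lower dose.

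**3. Rounding at the cut.** With 0.1 intended at 0.5 mmol/mL, the volume is 0.1*w*/0.5 = *w*/5 mL. Round it to the nearest whole mL for whole-kg weights:

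- *w* a multiple of 5: no rounding, dose exactly 0.1.
- Remainder 1 or 2: volume rounded down, dose below 0.1.
- Remainder 3 or 4: volume rounded up, dose above 0.1.

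The split is therefore about 40% below, 20% at and 40% above. Simulated weights (mean 75, SD 15, limited to 40 to 130 kg) gave 39.9% above and 20.1% exactly at 0.1, with doses from 0.0952 to 0.1047. For example, 15 mL is 7.5/74 = 0.1014 at 74 kg (upper bin) and 7.5/76 = 0.0987 at 76 kg (lower bin).

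**4. Sensitivity to the rounding assumption.** Giving each whole-kg weight from 45 to 110 kg equal weight (66 values), the share above 0.1 is:

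| Concentration and step | Nearest | Rounded up |
|---|---|---|
| 0.5 mmol/mL, 1 mL | 26/66 = 39% | 52/66 = 79% |
| 1 mmol/mL, 1 mL | 35/66 = 53% | 59/66 = 89% |

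A 0.5 mL step gives 39% and 79% at either concentration. Across all these cases doses lie between 0.093 and 0.118.

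**The case against.** The strongest reply is that the categories are an extra. 7.1.7 says dose is also categorised, after planning dose itself in several strata. These include field strength, the one driver that 1.1 ties to reductions, which Table 7.7 covers. Reductions that cross 0.1, 0.2 or 0.3 do change bin. The study is descriptive, and no passage defines a reduced dose or promises a percentage. All of this stands. A reader might infer that the plan as a whole cannot show dose reductions, or cannot show them by field strength, and the SAP does not support that.

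A reader might also take 0.1 as the standard dose, or take 40% as the share of this study's patients who will be misplaced. The SAP names no standard dose. The weights, the rounding step and the uniform intended dose are all assumed, and 3.2.1.5 records volume in mL without saying to what precision.

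Two further replies help only in part. SAP 5.3 stratifies endpoints by field strength where applicable, but the list in 7.1.7 is specific, Appendix 1 shows no separate table of dose categories by field strength, and 5.3 does not name GFR, age group or indication. Tables 7.16 to 7.20 are titled simply as injection dose, so a continuous summary is not excluded from them. However, the text that defines these strata commits only to the categories.

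**Conclusion.** The point holds in a limited form. The categorised analysis cannot show variation or reductions below 0.1 mmol/kg. This follows from the cut-points alone and does not depend on 0.1 being a usual dose, though how many patients it affects does. It matters most for GFR, age group and indication, where 7.1.7 commits to no other dose summary. In the other strata, including field strength, the continuous summary would show a shift but not the proportion of lower doses.

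The rounding sensitivity is real. Its size (about 40% just above the cut, or 39% to 89% across the rounding rules tried) rests on the assumptions stated and is no estimate for this study. This is a reporting weakness in a descriptive study and invalidates no other analysis.

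**What to change.** In SAP 7.1.7 and Appendix 1:

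1. Subdivide the ≤0.1 category.
2. Do not leave a bare cut at exactly 0.1. Use a tolerance band, or state how the derived dose is rounded before it is categorised, and treat any new cut-point the same way, since it would meet the same problem. Rounding to the nearest step shifts dose by at most (step/2) × concentration / weight. For a 1 mL step at 0.5 mmol/mL that is 0.25/75 = 0.0033 at 75 kg and 0.25/45 = 0.0056 at 45 kg, and twice as much at 1 mmol/mL. The band should be chosen with the recording precision and the range of weights in mind.
3. Give the continuous dose summary also by GFR, age group and indication (Tables 7.18 to 7.20).
4. Add scanner field strength to the strata for categorised dose.

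These are reporting categories only and imply nothing about which dose should be given. Volume, weight, agent and field strength are already collected. The cost is SAP wording, a few more table rows and one more table.

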1.2 Purpose of the analyses

The study is set-up for descriptive purposes, no a priori hypothesis will be tested.

The statistical analysis plan (SAP) is a more detailed description of the statistical rationale and the methods used for generating the results of this observational study.

It contains additional information not covered by the study protocol (Version 1.5, 28-Nov-2018).

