2 STUDY OBJECTIVES AND ENDPOINTS

2.1 Study objectives

Primary objectives:

The primary objective of the GBCA observational study, will be to prospectively collect data on the pattern of use for GBCA in real-life setting with special reference to Clariscan after its commercial launch in Europe.

Secondary objectives:

The study will look at the effectiveness and safety profile of GBCAs including Clariscan in clinical practice

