3 STUDY METHODS

3.1 Study design and plan description

This is a prospective, multi-center observational study.

It is planned to enroll up to 5400 patients from 7 countries and 14 sites.

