4 SAMPLE SIZE CALCULATION

The sample size is not based on statistical considerations, as the study does not formally test a hypothesis.

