APPENDIX 1: LIST OF TABLES/FIGURES/LISTINGS

Table	1.1	Subject disposition and analysis populations
Table	1.2	Subject disposition and analysis populations by site
Table	1.3	Subject disposition and analysis populations by specialty
Table	2.1	Observation period
Table	2.2	Observation period by site
Table	3.1	Demographics and baseline characteristics
Table	3.2	Demographics and baseline characteristics by site
Table	3.3	Demographics and baseline characteristics by specialty
Table	3.4	Demographics and baseline characteristics by GBCA
Table	3.5	Main reason for using contrast media by GBCA
Table	4.1	Medical history
Table	4.2	Medical history by site
Table	4.3	Medical history by GBCA
Table	4.4	Number and frequency of previous scans by country
Table	5.1	Funding
Table	5.2	Funding by country
Table	5.3	Funding by specialty
Table	5.4	Funding by GCBA
Table	6.1.1	Referral
Table	6.1.2	Referral by site
Table	6.1.3	Referral by country
Table	6.1.4	Repeat scans by type of referral
Table	6.2.1	Repeat scans by type of referral by site
Table	6.2.2	Repeat scans by type of referral by country
Table	6.2.3	Repeat scans by type of referral by specialty
Table	6.2.4	Repeat scans by type of referral by GBCA
Table	7.1	Injection and scanning
Table	7.2	Injection and scanning by site
Table	7.3	Injection and scanning by country
Table	7.4	Injection and scanning by specialty
Table	7.5	Injection and scanning by GBCA
Table	7.6	Injection and scanning by scanner type
Table	7.7	Injection and scanning by scanner field strength
Table	7.8	Injection and scanning by scan modality
Figure	7.9	Bar chart of mean volume of contrast agent for type by sequence
Figure	7.10	Bar chart of mean volume of saline follow-up injection by type of sequence
Table	7.11	Sequence type by injection protocol
Table	7.12	Sequence type by injection protocol by site
Table	7.13	Sequence type by injection protocol by country
Table	7.14	Sequence type by injection protocol by age groups
Table	7.15	Sequence type by weight
Table	7.16	Injection dose
Table	7.17	Injection dose by GBCA
Table	7.18	Injection dose by indication
Table	7.19	Injection dose by age group
Table	7.20	Injection dose by GFR rate
Table	8.1	Diagnostic impact

Table	8.2	Diagnostic impact by site
Table	8.3	Diagnostic impact by specialty
Table	8.4	Diagnostic impact by GBCA
Table	8.5	Precision of the diagnostic criteria
Table	8.6	Precision of the diagnostic criteria by site
Table	8.7	Precision of the diagnostic criteria by specialty

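### Dose by scanner field strength is planned only as an unadjusted one-factor summary, so a different mix of indications or agents could mask or mimic a dose difference

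*SAP*

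**What the plan says.** Section 1.1 of the SAP sets out what is not known about current practice, and one sentence reads: "Also, it is unknown if dose reductions, perhaps dependent on scanner magnetic field strength, are applied". The paragraph that follows says the data collected will help to clarify these points. The objectives in section 2.1 do not name field strength; the primary one is to "prospectively collect data on the pattern of use for GBCA in real-life setting". Section 1.2 adds: "The study is set-up for descriptive purposes, no a priori hypothesis will be tested".

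Section 3.2.1.5 records "Field strength (1.5T, 3T, >3T") for each examination, together with the brand, the volume and an indication in three classes (CNS, organ/whole body, angiography).

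Section 7.1.7 plans two analyses of dose:

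- Volume, dose in mmol/kg and the other injection variables are summarised by one factor at a time, and field strength is one of these factors. The output is Table 7.7, "Injection and scanning by scanner field strength".
- Dose in four categories is shown "for all patients (FIP), by GBCA (GBCAP), by age groups (FIP), by GFR rate (GFRP), and by indication (see 3.2.1.5"). Tables 7.16 to 7.20 match this list, and field strength is not in it.

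For stratified comparisons, section 7 adds exploratory ANOVA or Chi-Square tests where feasible and names no covariates. Section 5.8 declares p<0.05 statistically significant. Section 5.3 lists field strength among general stratifiers where applicable, again as a single factor.

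**The concern.** Table 7.7 compares all examinations on 1.5T scanners with all examinations on 3T scanners. The plan gives dose its own tables by GBCA (7.17) and by indication (7.18), so it expects dose may vary with both. If scanners of different field strength serve different examinations or stock different agents, the crude comparison mixes any field-strength difference with that case mix. No listed table crosses field strength with indication or GBCA, and no adjusted model is planned, so the outputs could not show which of the two is at work.

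At stake is how one question from the rationale is read. With a test attached and several thousand patients, a small case-mix difference could be reported as a significant dose difference between field strengths, or a real one could go unseen.

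**Working it through.** **No plan figure to reproduce.** The SAP gives no effect size, standard deviation or power: "The sample size is not based on statistical considerations, as the study does not formally test a hypothesis". The check therefore compares the text with the table list and adds an illustration on assumed inputs.

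**Outputs that bear on the question**

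| Output | Dose scale | Split by |
|---|---|---|
| Table 7.7 | continuous | field strength only |
| Table 7.17 | categories | GBCA only |
| Table 7.18 | categories | indication only |
| Tables 7.16, 7.19, 7.20 | categories | none; age group; GFR |

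Nothing listed shows dose by field strength within indication or within GBCA.

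**Illustration (all inputs assumed, none from the SAP).** Take two classes of indication with mean dose 0.10 and 0.10 + g mmol/kg. Let q be the share of the higher-dose class at each field strength, and r the true reduction at 3T within each class.

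- Crude mean at 1.5T = 0.10 + g × q(1.5T)
- Crude mean at 3T = 0.10 + g × q(3T) − r
- Apparent reduction = r + g × [q(1.5T) − q(3T)]

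The second term is the case-mix bias. It vanishes if g = 0 or if the shares are equal.

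| g | q at 1.5T | q at 3T | True r | Crude 1.5T | Crude 3T | Apparent reduction |
|---|---|---|---|---|---|---|
| 0.05 | 10% | 30% | 0 | 0.105 | 0.115 | −0.010 (an increase) |
| 0.05 | 30% | 10% | 0 | 0.115 | 0.105 | 0.010 (mimicked) |
| 0.05 | 10% | 30% | 0.010 | 0.105 | 0.105 | 0.000 (masked) |
| 0.02 | 30% | 10% | 0 | 0.106 | 0.102 | 0.004 |
| 0.02 | 10% | 30% | 0.010 | 0.102 | 0.096 | 0.006 |
| 0.10 | 30% | 10% | 0 | 0.130 | 0.110 | 0.020 |
| 0.10 | 10% | 30% | 0.020 | 0.110 | 0.110 | 0.000 |

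Compared within each class, the difference equals r in every row.

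**Would the test flag a pure case-mix difference?** The plan states: "It is planned to enroll up to 5400 patients from 7 countries and 14 sites". Assume all 5400 have a dose and fall in two field-strength groups, 30% to 50% at 3T, with SD 0.03 to 0.05 mmol/kg, independent patients and a two-sided test (the SAP does not state sidedness). Then SE = SD × √(1/n(1.5T) + 1/n(3T)), and the chance of p<0.05 is about Φ(difference/SE − 1.96). For a difference of 0.004:

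- SD 0.05, 3780 and 1620 patients: SE = 0.05 × √(1/3780 + 1/1620) = 0.00148; 0.004/SE = 2.69; chance 0.77.
- SD 0.03, 2700 and 2700 patients: SE = 0.03 × √(2/2700) = 0.00082; 0.004/SE = 4.90; chance 0.998.

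Over the same ranges the chance is 0.27 to 0.69 for a difference of 0.002, and above 0.99 for 0.010.

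**Would adding field strength to the dose categories help?** Little. Every dose at or below 0.1 mmol/kg is one category, so a lowering within that range does not register. With an assumed normal dose distribution of mean 0.09 and SD 0.01, 84% of patients are in that category before any reduction.

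**The case against.** The strongest reply is that dose by field strength is already planned, and in its more informative form. Section 7.1.7 names it, Table 7.7 delivers it, and section 7 adds a test. Dose is expressed per kg and allows for the higher concentration of one agent, so body weight and concentration are already dealt with. The study is descriptive, the question stands only in the rationale and is hedged there, and one-factor summaries are the design of almost the whole SAP. The doses and shares in the illustration are invented, and nothing in the SAP shows that case mix differs between field strengths.

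Most of this stands, and it rules out two stronger readings. A reader might infer from the dose-category list that dose is not analysed by field strength. That is wrong for continuous dose, and the omission from the categories matters little. A reader might also infer that the study can give no valid answer. The documents do not support that: which doses are given on 1.5T and on 3T scanners is a pattern-of-use question, and a crude summary answers it.

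The layout of Table 7.7 is also not fully known. Section 3.2.1.5 records MRI and MRA details separately and no table shells are shown, so the table might separate them. Section 7.1.7 lists MRA/MRI as its own factor, with its own Table 7.8, which suggests that it does not. Even if it did, CNS against organ/whole body, and agent, would stay pooled.

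The reply does not meet one point: the rationale asks whether reductions depend on field strength, and the plan attaches a significance rule to a comparison that cannot separate this from case mix on factors it already records.

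**Conclusion.** The point holds as a limit on interpretation and a worthwhile, inexpensive improvement; it does not make a planned analysis invalid. Table 7.7 describes the doses used at each field strength. Alone, it cannot support a statement that dose is, or is not, lowered because of field strength.

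The size and direction of any distortion are unknown. Under the assumptions shown it ranges from 0.004 to 0.020 mmol/kg either way, and about 0.01 in the central case. It requires that dose differs between indications or agents and that their mix differs by field strength. The plan's own tables make the first plausible; the documents are silent on the second.

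**What to change.** In section 7.1.7 and Appendix 1, add a table of continuous mmol/kg dose by field strength within each indication (CNS, organ/whole body, angiography) and within GBCA. Alternatively, report the field-strength difference, with a confidence interval, from a linear model of dose on field strength, indication and GBCA, labelled exploratory. Base any statement on field-strength-dependent dosing on this output, and label Table 7.7 as unadjusted. Adding field strength to the dose-category tables is optional.

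The cost is one or two tables or one model, and all variables are already collected. Some cells, such as >3T, will be sparse and can stay descriptive. The change removes case mix on indication and agent only; differences between sites or age groups may remain and should be acknowledged.
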